### **VI. Number of Subjects**

1. We plan to enroll 230 participants (n=230 subjects) (100 subjects per group, 30 screen fails) for a 2-year study. This will allow complete data for at least 200 who will complete the one-year follow-up.
2. This sample size was determined by a pre-study power analysis based on 10% reduction in 90-day SSI incidence with a desired power of 0.8 and alpha set at <0.05.

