### **VII. Study Procedures/ Design/Treatment Plan**

1. Randomization Process
  - a. After informed consent is obtained, all patients who meet eligibility criteria will be randomized into one of two groups. Randomization will be achieved by numbering 230 sealed envelopes (115 Irrisept, 115 Normal Saline). There is no blinding to the randomization. It would be difficult to blind the participants or research personnel.
  - b. Standard of care at this institution is irrigation with normal saline and debridement.
  - c. If randomized to the Irrisept group, patients will be removed from standard of care.
2. Surgery
  - a. Patients will be screened and randomized prior to going to the operating room for the initial operative debridement of the open tibia fracture. They will return to the operating room for as many operative debridements as necessary until the definitive fixation surgery is performed.
  - b. One group will utilize only Irrisept solution for all open fracture debridements and irrigations, and the other will utilize only normal saline for all debridements and irrigations. Surgical sites that are not the open fracture site should be irrigated with normal saline as per standard of care.
  - c. The subjects will undergo standard operative debridement and fixation.
  - d. All other components of the management will be standard—antibiotics pre- and postop, surgical debridement, dressings/use of negative pressure wound therapy, etc.
3. Clinical Follow-Up
  - a. Standard of Care Standard of Care (SOC)—2 weeks, 6 weeks, 3 months, 6 months and 1 year with tibia radiographs at each visit except the 2-week follow up. Study window will be +/- 2 weeks starting at the 6-week visit.
  - b. Tibia radiographs will be collected at each visit per SOC to assess fracture healing as 0-not healed; 1-partially healed; or 2-completely healed.
  - c. Deep infection rate as well as wound healing will be assessed. Developing infection would be monitored regardless of the subject's participation in the study.
  - d. Patient reported outcomes including PROMIS and VAS pain scores will be collected at each visit per SOC.
  - e. Subjects will be monitored at follow-ups for unanticipated events.
4. Subjects will be removed if they do not return to their follow-up visits or do not complete the study specific tasks.
5. Subjects that are removed prematurely or complete the study will continue routine care per physician's standard of care treatment.

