6. No specimens will be collected for research purposes.
7. Statistical Analysis – significance set at  $p < 0.05$ .
  - a. Primary Outcome Measure: CDC-defined 90-day surgical site infection (SSI) incidence – compared among groups using chi-square test.
  - b. Secondary Outcome Measure: Fracture healing at 6 months post-op – compared between groups using a rank sum test.

- c. Secondary Outcome Measures: PROMIS and VAS Pain scores – compared between groups using unpaired t-Tests.
- d. Secondary Outcome Measure: Multivariate analyses will be used to assess the effects of severity grade (type I vs II vs II open) on deep infection rates in open tibia fractures.

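### The six-month healing comparison states no effect estimate and ignores severity grade, so it loses power if grade predicts healing

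*Combined protocol and SAP*

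**What the plan says.** Section I.2 lists fracture healing at 6 months as the first secondary objective. Section VII.3.b has radiographs read "to assess fracture healing as 0-not healed; 1-partially healed; or 2-completely healed". Section VII.7.b gives the whole analysis: the six-month result is "compared between groups using a rank sum test". No effect measure, confidence interval, category percentages or covariate is named.

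Severity grade enters the analysis plan only in VII.7.d, in a multivariate analysis of deep infection. There, as in the Background (I.1), the list of grades gives type II twice.

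The sample size in section VI ("100 subjects per group, 30 screen fails") is tied to infection alone: "This sample size was determined by a pre-study power analysis based on 10% reduction in 90-day SSI incidence". No power is stated for healing.

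**The concern.** There are two separate gaps.

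- **Reporting.** As written, the plan commits to a test of healing but to no measure of how far the arms differ. The trial is not sized for healing, so a non-significant result is quite possible. Without an estimate and interval, a reader could not tell a small difference from an imprecise one.
- **Efficiency.** A plain two-sample rank sum test pools all fracture severities. If more severe open fractures heal more slowly, that variation obscures the comparison between arms. The trial will hold severity grade anyway for VII.7.d, so the lost power could be recovered without new data.

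**Working it through.** **Plan's own figure.** There is none for healing. The 100 per group comes from a "10% reduction in 90-day SSI incidence", with no control rate given, and has no bearing on this endpoint. It is used here only as the number analysed per arm.

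**Inputs from the documents.** Three-level score (VII.3.b); rank sum test (VII.7.b); 100 per arm (VI); alpha 0.05 (VI and VII.7), taken as two-sided because sidedness is not stated.

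**Assumptions, because the documents are silent.** Treatment odds ratio 2; odds ratio per grade step 1 to 5; three grades; and the following distributions for scores 0/1/2 in controls and for grade:

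- A: control 20/40/40%, grades 25/35/40%
- B: control 20/40/40%, grades equally frequent
- C: control 10/30/60%, grades equally frequent

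In B and C the control percentages apply at the middle grade.

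**What an odds ratio of 2 means with 20/40/40%.** The odds of complete healing go from 0.4/0.6 = 0.667 to 1.333, so 40% becomes 1.333/2.333 = 57%. The odds of no healing go from 0.2/0.8 = 0.25 to 0.125, so 20% becomes 0.125/1.125 = 11%.

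**Tests compared.**

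- Rank sum: Z = (W − n₁(N+1)/2)/√V, with V = (n₁n₀/12)[(N+1) − Σ(t³−t)/(N(N−1))], where t are the numbers tied at each score.
- Proportional odds: logit P(Y ≤ j) = αⱼ − β·arm − γ(grade). The common odds ratio is exp(β), and arm is tested by the likelihood ratio against 3.84.
- Rank sum stratified by grade (van Elteren).

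**Power (%), plain rank sum → analysis using grade, with the gain in points.** B and C have 1,500 simulated trials per scenario and use the grade-adjusted proportional-odds model. B was run twice.

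| OR per grade | A | B, run 1 | B, run 2 | C |
|---|---|---|---|---|
| 1.5 | 71→72 (1) | 69.7→72.1 (2.4) | 69.8→72.7 (2.9) | 62.6→64.4 (1.8) |
| 2 | 68→72 (4) | 66.8→71.9 (5.1) | 67.5→72.2 (4.7) | 60.3→63.2 (2.9) |
| 3 | 61→70 (9) | 60.1→70.4 (10.3) | 58.5→67.9 (9.4) | 53.8→61.7 (7.9) |
| 5 | 51→68 (17) | 49.4→67.9 (18.5) | 48.9→65.9 (17.0) | 44.7→59.3 (14.6) |

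Averaging the two runs of B, for example (18.5 + 17.0)/2 = 17.75, the gains are about 1 to 3 points at 1.5, 3 to 5 at 2, 8 to 10 at 3 and 15 to 18 at 5.

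**No grade effect (OR 1).** B gives 72.5% for rank sum and 72.7% for the adjusted model; C gives 60.5% and 60.6%. In A, using grade costs under 1 point.

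**Where the gain comes from.** The proportional-odds model without grade gains only 0.1 to 0.7 points over the rank sum test (B, run 1, OR 3: 60.1% and 60.3%). The rest comes from grade. The stratified rank sum test recovers most of it: in B, run 2, at OR 3 it reaches 67.1%, against 67.9% for the adjusted model and 58.5% for the plain test. In B, run 2, and in C it stays within 0.8 to 1.4 points of the adjusted model.

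**Type I error.** With no treatment effect, the adjusted test rejected in 4.5 to 5.8% of trials. The simulation error is √(0.05 × 0.95/1500) = 0.6 points.

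**The case against.** The strongest reply is that nothing here is wrong. A rank sum test is a standard, valid choice for a 0/1/2 score. The protocol sets no power target for healing, and naming a test does not forbid reporting percentages by arm. VII.7.a and VII.7.c also name only tests, so the missing estimate is not peculiar to healing. All of that stands, and it is why the point ranks as an improvement.

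Three stronger readings are tempting, and none holds:

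- **That the proportional-odds model is itself more powerful.** It is not. Without grade it performs almost exactly like the rank sum test.
- **That a rank sum analysis can yield only a p-value and can take no account of grade.** It can report the Mann-Whitney probability of a better score with an interval, and it can be stratified. The gap lies in what VII.7.b specifies, not in the method.
- **That the one-year score wrongly goes uncompared.** The objective in I.2 is healing at 6 months, and VII.7.b analyses that. Keeping to one pre-specified time is sound.

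Two objections to using grade also have force. Its levels are not properly defined while type II appears twice. The documents do not say when, or by whom, grade is recorded, and under VII.1 and VII.2 the trial is unblinded and randomizes before the first debridement. A grade assigned at surgery could therefore be judged by staff who know the allocation. Both must be settled before grade is used.

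**Conclusion.** The point holds as an efficiency and reporting improvement to a secondary endpoint. That VII.7.b gives no estimate and no adjustment is plain from the text and rests on no assumption.

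The size of the power loss does rest on assumptions: 100 per arm, treatment odds ratio 2, and the healing and grade distributions listed above. Under these it is about 1 to 5 points at an odds ratio per grade of 1.5 to 2, about 8 to 18 points at 3 to 5, and none if grade is not prognostic. The documents do not show which case applies. The asymmetry favours using grade: the possible gain is material, the cost if grade proves uninformative is under 1 point, and the type I error stays near 5%.

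**What to change.** Replace VII.7.b with wording such as:

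> The six-month healing score (0/1/2) will be compared between arms by proportional-odds logistic regression with arm and severity grade as terms. The common odds ratio with 95% CI will be reported, with the percentage in each category by arm.

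If the investigators prefer a rank method, a rank sum test stratified by grade gives a similar power gain. An effect measure with an interval and the category percentages should then be reported beside it.

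Two things come first:

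1. Correct the list of grade levels in VII.7.d, and in the Background where it is repeated.
2. State when and by whom grade is recorded, and use the grade recorded before the allocation is known, or at least before study irrigation.

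**Cost.** A few sentences, with the same radiographs and scores. There are two downsides to state. The common odds ratio assumes proportional odds, which is why the category percentages are shown beside it. It is also conditional on grade, so it will generally differ from the unadjusted odds ratio if grade is prognostic.

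### PROMIS and VAS scores from five visits go to unpaired t-tests at p < 0.05 with no visit, PROMIS domain or multiplicity rule named, and partial follow-up goes unused

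*Combined protocol and SAP*

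**What the plan says.** Section VII.3.a schedules follow-up at "2 weeks, 6 weeks, 3 months, 6 months and 1 year". Section VII.3.d adds: "Patient reported outcomes including PROMIS and VAS pain scores will be collected at each visit per SOC". That makes five scores per instrument for a patient who attends throughout.

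The whole analysis plan for these outcomes is in VII.7.c: they are "compared between groups using unpaired t-Tests". Item VII.7 opens with one general threshold, "significance set at" p < 0.05. Neither VII.7 nor the objectives in section I.2 names a visit or a PROMIS domain. No multiplicity rule, repeated-measures model or missing-data method appears. Fracture healing, the other secondary outcome listed in I.2, is fixed at 6 months in both places.

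On incomplete follow-up, VII.4 states: "Subjects will be removed if they do not return to their follow-up visits". It extends this to patients who do not complete study tasks, and it does not say whether scores already collected are kept. Section VI gives no dropout rate. It plans for full data at one year on 200 or more patients.

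**The concern.** An unpaired t-test takes one independent score per patient, and here there are up to five. The plan does not say whether each visit is tested, one visit is used, or visits are combined. Testing every visit at 0.05 raises the chance of a spurious finding. So does settling on a visit once the data are in hand. Pooling the visits as if they were independent would break the test's assumptions.

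The second issue is separate. A t-test at any one visit uses only the patients seen at that visit. Someone who attended through 3 months and then stopped contributes nothing to a 6-month or 1-year comparison, although the earlier scores carry information about the later ones. The removal rule in VII.4 makes this more likely to matter. The trial is unblinded (VII.1.a), so attendance could depend on recovery differently in the two arms, and a comparison of attenders alone could then be biased.

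At stake are the patient-reported secondary results: a false claim of a difference between irrigants, or an estimate that is less precise or less secure than the collected data allow.

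**Working it through.** The plan states no power, effect size or standard deviation for PROMIS or VAS, so there is no figure of its own to reproduce here. Its power calculation in section VI is "based on 10% reduction in 90-day SSI incidence" and concerns the primary endpoint only.

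**Inputs from the documents.** Five visits (VII.3.a); two instruments (VII.3.d, VII.7.c); threshold 0.05 (VII.7); 100 per group (VI). **Assumed, not in the documents.** Two-sided tests, the correlations between test statistics, and the dropout patterns.

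**1. Number of tests.** 2 instruments × 5 visits = 10 if every visit is tested, with each further PROMIS domain adding 5. With one visit per instrument there are 2.

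**2. False positives with no true difference.** For k independent tests, the chance of at least one result in either direction is 1 − 0.95^k. For a result favouring one given arm it is 1 − 0.975^k. The correlated values come from simulating 10 normal test statistics with a common correlation.

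| Scenario | Either direction | Favouring one given arm |
|---|---|---|
| 10 tests, independent | 1 − 0.95^10 = 40.1% | 1 − 0.975^10 = 22.4% |
| 10 tests, correlation 0.5 | about 29% | about 14% |
| 10 tests, correlation 0.7 | about 21% | about 11% |
| 2 tests, independent | 1 − 0.95^2 = 9.75% | 1 − 0.975^2 = 4.9% |

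Allowing different correlations between visits and between instruments (0.3 to 0.8 each) gives 19-37% in either direction and 10-19% favouring one given arm.

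**3. Choosing the visit afterwards.** If the most favourable of five visits is picked for one instrument, the error equals that of testing all five: 1 − 0.95^5 = 22.6% if independent, and about 18% and 15% at correlations of 0.5 and 0.7.

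**4. Precision lost to absent patients.** Take 100 per arm and equal correlation between visits. Let missing data accumulate from none at 2 weeks, in roughly equal steps, to 12% (or 20%) at 6 months and then 20% (or 30%) at 1 year. The t-test variance per arm is proportional to 1/(number observed at that visit). The repeated-measures variance is the matching diagonal entry of the inverse information, summed over dropout patterns. For correlations of 0.5-0.7, the t-test variance is larger by:
- 4-13% at 6 months, so the standard error is larger by √1.04 to √1.13, or about 2-6%;
- 8-22% at 1 year, so the standard error is larger by √1.08 to √1.22, or about 4-10%.

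Other dropout patterns gave as little as 3% and 6% in variance.

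**5. Check by hand with two visits.** The variance factor for the likelihood analysis is 1 − ρ²d. With dropout d = 0.2 and ρ = 0.7 this is 1 − 0.49 × 0.2 = 0.902. The 80 observed patients per arm then act like 80/0.902 = 88.7. At an assumed standardized difference of 0.4, power is 0.76 against 0.72. With d = 0.1 and ρ = 0.5 the gain is about one point of power.

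**The case against.** Most of the case on the other side concerns how far the point reaches, and much of it stands.

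- A reader might infer that the plan prescribes at least 10 tests. It does not. VII.3.d says the scores are collected at each visit, not that each visit is tested. One test per score at a single visit fits VII.7.c equally well. Ten is the count if every visit is tested and PROMIS yields one score.
- A reader might take 40% as the chance of wrongly claiming a benefit for Irrisept. That figure assumes independence and counts errors in both directions. For a false result favouring one given arm, the figures are 22% if independent and 11-14% at the correlations used.
- A reader might blame the t-test for the inflation. The inflation comes from the unnamed visit and the missing multiplicity rule. A t-test at one pre-named visit would remove most of it and is a legitimate, simpler choice. A mixed model with no named contrast would permit the same 10 tests.
- A reader might infer that a t-test on attenders is unbiased only if absence is completely random. That is too strong. Absence unrelated to score within each arm does no harm, and under no effect a mechanism identical in both arms leaves the difference unbiased. The risk arises when absence depends on earlier scores differently by arm.
- The dropout rates are assumed, and section VI expects 200 or more patients complete at one year. If that is achieved, the precision argument shrinks.

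What remains is that the plan fixes none of visit, domain or error control, and gives no way to use partial follow-up although VII.4 anticipates non-returners.

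**Conclusion.** The point holds in a limited form. VII.7.c leaves open how five repeated scores become one comparison, so the false-positive risk across PROMIS and VAS could be anywhere from 9.75% or less (one pre-named visit per score) to 40% (ten independent tests), with about 21-29% for ten tests at correlations of 0.7-0.5. More PROMIS domains would raise it. These figures rest on assumed correlations and on the reading that every visit is tested or the visit is chosen late. The documents neither state nor exclude that reading.

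The loss from ignoring partial follow-up is real but modest under the assumed dropout, and it would be smaller if section VI's expectation is met. Possible bias in an unblinded trial is the weightier reason to use all observed scores, but nothing in the documents allows its size to be estimated.

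These are secondary outcomes and the primary chi-square test keeps its own 0.05. This is a worthwhile, inexpensive improvement to make before outcome data are examined, and not a threat to the trial's main conclusion.

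**What to change.** Replace the t-tests in VII.7.c with one linear mixed model for repeated measures per score, with terms for group, visit, group-by-visit and fracture type, and an unstructured within-patient covariance. Use every observed score from all randomised patients, including scores collected before a patient is removed under VII.4.

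In the same paragraph:
- name the PROMIS domain(s);
- name one key visit, for example 6 months to match the healing endpoint;
- either share alpha across the key contrasts, for example by Holm, or label them exploratory;
- report the other visits as estimates with 95% confidence intervals and no significance claims.

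With two key contrasts, Holm or Bonferroni holds the overall error at 5% or less. The price at 100 per arm and 80% power, under Bonferroni, is a rise in the detectable standardized difference from (1.960 + 0.842) × √(2/100) = 0.396 to (2.241 + 0.842) × √(2/100) = 0.436. Bonferroni over all 10 tests would need 0.516.

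The change takes one paragraph and slightly more programming, with no new data or visits. Visits other than the key one can no longer be claimed as significant. The model still assumes data are missing at random, so it does not remove bias when absence depends on unobserved scores.

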## **VIII. Potential Risks/Adverse Events**

1. Risks
  - a. Risks for breach of confidentiality does exist but will be limited with tight control of data and limited access to the investigators/study team.
  - b. There is a minimal increased risk of reaction to chlorhexidine gluconate in the Irrisept treatment group which may include allergic reaction or irritation.
2. Any complications arising from the use of the Irrisept irrigation will be reported to the IRB within 5 days.

## **IX. Anticipated Benefits**

1. There is no guarantee of direct benefit to study participants.
  - a. The data collected will contribute to the orthopaedic knowledge base. We hope it can be implemented to provide improved evidence-based care of these injuries.
  - b. Potential benefits include possible lower risk of infection and decreased overall healthcare costs.

## **X. Compensation**

1. No compensation will be provided to the subjects.

## **XI. Costs**

1. No research specific costs will be incurred by the research subjects.
2. Standard of care procedures will be billed to the insurance/third party payor/participant.

The costs associated with this study are outlined below:

1. Cost of research support (IRB submission and maintenance, storage and management of study documents, statistical support) = \$50,000
2. IRB Fees = \$5,500.00 (\$2,500 Initial Approval + \$1,500.00 Annual Review)
3. Cost of product (\$65 x 200 in experimental group) = \$ 13,000– Budgeting for 2 bottles of Irrisept solution per case.

## **XII. Data Safety Monitoring Plan**

1. Patient confidentiality during the course of this study will be protected in compliance with HIPAA requirements as well as the requirements of the University of Missouri Health-Sciences IRB.

2. All subjects will be assigned a study identification number that requires the use of a key in order to decipher a subject's personal identification information. The key will be kept in a secure electronic location, which is password protected. The study identification number will be used to label all paper data collection instruments.
3. All subject information in electronic format will be kept in password-protected storage. All subject information in paper format will be kept in locked cabinets in a secured suite at the Missouri Orthopedic Institute, and otherwise will be archived in a secure storage facility or destroyed.
4. Data will be stored on the Department of Orthopaedic Surgery shared drive and/or PatientIQ, a HIPAA-compliant cloud-based platform that is contracted with the department of orthopaedic surgery.

